#### 4.1.3 CASPALLO Trial

In a Phase I study, ten patients between the ages of 3 and 17 years who had undergone stem-cell transplantation for relapsed acute leukemia were treated with the genetically modified T cells. The cells were detected in peripheral blood and increased in number over time, despite their constitutive transgene expression. A single dose of dimerizing drug, rimiducid, given to the patients in whom GVHD developed, eliminated more than 90% of the modified T cells within 30 minutes after administration and a greater than 90% reduction in CD19+ (i.e. transduced) T cells within 30 minutes of drug administration, and a further log reduction within 24 hours without any reports of infusion toxicity. Moreover, acute GVHD of the skin in all three patients, and of the liver disease in one patient, completely resolved after 24 hours. (Di Stasi 2011). The patients who developed GVHD received rimiducid. None of the 10 patients developed cGvHD. Six of the 10 patients are alive to date, with relapse as the primary cause of death in the other 4 patients (Zhou 2014).

The residual iCasp9 gene modified T cell population expanded over the next 4-14 days and continued to help repopulate the patients' immune systems. The transduced cells were further shown to contain virus and fungal-peptide specific precursor cells which had not caused further GVHD. When examined ex vivo, these non-alloreactive iCasp9 T cells remained susceptible to apoptosis following exposure to the dimerizer rimiducid. The authors concluded that a single dose of dimerizer drug could eliminate the subpopulation of T cells causing GVHD but could spare viral specific cytotoxic T lymphocytes (CTL)s.

The iCasp9 gene is most highly expressed in activated and proliferating T cells, such as those causing GVHD. If cells are not activated, due to lack of viral stimulation for example, expression of the transgene is lower and in a minority of these cells, iCasp9 levels are insufficient to induce apoptosis after single rimiducid dose exposure, allowing subsequent re-expansion (Berger 2004). This hypothesis was supported by the CASPALLO clinical data showing activation-dependent

induction of iCasp9 in T lymphocytes and enhanced susceptibility to dimerizer drug in activated versus resting T cells.

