## Appendix B: Management of Chronic GVHD (cGVHD)

Event	Management
cGVHD - Mild	
 
• Consider tissue biopsy to establish diagnosis
 
• Initial treatment with topical or IV steroids, or other systemic treatments (eg, calcineurin inhibitors), per institutional standard of care for mild cGVHD should be instituted. Guidelines for topical corticosteroid treatment include the following (Couriel 2006): 
 
◦ Face, axillae, and groin: lower potency steroids (hydrocortisone 1-2.5%, desonide 0.05%)
 
◦ From the neck down: mid-strength steroids (e.g., triamcinolone 0.1% cream or ointment)
 
 
 
• Systemic corticosteroids when used should be administered as methylprednisolone 2 mg/kg/day IV in a single dose; or a dose equivalent of prednisone or dexamethasone (Martin 1990; see also corticosteroid conversion table C below).
 
• If no response to steroids/systemic therapies occurs within 7 days, or there is a worsening in cGVHD, patients may then receive rimiducid: 
 
◦ Children: 0.4 mg/kg to a maximum of 40 mg IV
 
◦ Adults: 40 mg IV
 
◦ If there is evidence of clinical improvement (e.g. partial response) but not complete resolution after the first dose of rimiducid, then rimiducid may be repeated up to a total of 3 doses beginning 48 hours after the first dose, with each dose separated by 48 hours
 
◦ Daily examination on day 1 and day 2 should be performed after initiating treatment with rimiducid, then weekly for 1 month, every 2 weeks for 100 days, and monthly after 100 days post-rimiducid administration
 
◦ For new or recurrent cGVHD episodes, rimiducid may be considered for repeat administration with the above guidelines if the investigator considered rimiducid to offer clinical benefit with prior episodes.
 
 
 
• If no response to topical steroids or rimiducid, the investigator should consider other medications per institutional guidelines (eg, calcineurin inhibitors, sirolimus, mycophenolate).
 
• Peripheral blood will be used to evaluate BPX-501 cells (CD3+CD19+) at the following times: 
 
◦ Prior to administration of systemic corticosteroid doses (e.g. methylprednisolone), at 4 and 24 hours (<math>\pm</math> 30 minutes) post-systemic corticosteroid doses, and at 7, 14, 21 and 28 days (<math>\pm</math> 24 hours) post-systemic corticosteroid doses
 
◦ When possible, considering patient weight, blood samples will be drawn within 4 hours (<math>\pm</math> 30 minutes) prior to the initiation of rimiducid infusion; 30 mins (<math>\pm</math> 5 minutes) after initiation of the infusion; at 2 hours (< 5 min prior to end of the rimiducid infusion), 4 hours, 6 hours, 8 hours, 12 hours, and 24 hours (<math>\pm</math> 30 minutes) after the initiation of the infusion. Each sample collected out to 24 hours should be split for separate processing. Approximately 0.5 to 1 mL of blood should be processed to plasma and stored at -80 C for later PK analysis of rimiducid. The remaining samples, at least 0.3 mL of blood, should be analyzed locally for prompt CD3+CD19+ T cell analysis. These additional samples (at least 0.3 mL) will be drawn at 48 hours (<math>\pm</math> 30 minutes), then at 7 days (after initiation of infusion of each dose of rimiducid), and at 14 days, 21 days, and 28 days (<math>\pm</math> 24 hours) after the final dose of rimiducid (in
 
 
 

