6. STATISTICAL METHODS AND DATA HANDLING

6.1. Analysis Populations

The following analysis populations are defined for the study:

(i) *Enrolled Population (EP)* – Defined as all patients who signed informed consent, were assessed for inclusion/exclusion criteria during the screening period, and who were considered eligible for enrollment and post-enrollment follow-up. This population will be used to present overall study disposition data and for summarizing the total number of patients screened and considered eligible for the study.

(ii) *HSCT Safety Population (HSP)* – Defined as all patients in the enrolled population (EP) who received Hematopoietic Stem Cell Transplantation (HSCT). Only SAEs were reported in subjects prior to receiving BPX-501. The HSP therefore represents the analysis population for certain analyses of SAEs as well as disposition and outcomes in subjects who did not go on to receive BPX-501 for any reason.

(iii) *BPX-501 Safety Population (BSP)* – Defined as all patients who received HSCT and went on to receive any dose of BPX-501. Unless otherwise specified, this will be the default primary safety analysis population.

(iv) *Intent-to-treat Population (ITT)* – Given that this is a single-arm study, a “Full Analysis Set” (FAS) population is proposed to serve as the ITT population from which to provide estimates of treatment effects in subjects receiving BPX-501. The FAS/ITT population includes all patients treated with HSCT who received BPX-501 at the dose of 1×10^6 cells/kg.

(v) *Per Protocol Populations (PP)* – Defined as all patients in the ITT/FAS analysis population who were infused with BPX-501 at the dose of at least 1×10^6 cells/kg within a dosing around Day 14 (+/- 4 days) or Day 21 (+/- 14 days) after HSCT. The primary and key secondary efficacy analyses may be repeated on the PP populations as a means of characterizing the robustness of any outcome results.

(vi) *Rimiducid Population (RP)* – Defined as all patients who received at least one dose of rimiducid for the treatment of acute or chronic GvHD.

(vii) *Rimiducid Pharmacokinetics Population (RPK)* – Defined as all patients who received at least one dose of rimiducid for the treatment of acute or chronic GvHD and have a plasma sample to measure rimiducid concentrations over time.

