6.2.2. Missing Data and Handling of Dropouts

Unless otherwise specified, missing data will not be imputed for efficacy variables. For subjects who withdrew from the study prior to study completion, all data attained up to the point of discontinuation will be listed and included in data summaries. Patients will be censored at the time of their last documented study visit prior to or at the time of study withdrawal.

The term missing date refers to a completely missing date or to a partial date where month, day or year are missing. Unless otherwise stated, the handling of partial missingness of dates will impute using midpoint values. That is, missing days will be imputed as the 15th of the month and

missing months will be imputed as July 1st, unless a more suitable value can be imputed based on study or treatment start and end dates.

If an adverse event (AE) resolution date is completely missing, the duration (ongoing/resolved status) will be checked before imputing a date, noting when the AE started in relation to study treatments. If the ongoing flag is missing, then it is assumed that the AE is still present (i.e., do not impute a date).

Adverse event relationship missing: If the relationship for an adverse event is not recorded, it will be reported as missing in the presentation of listings and summaries of incidence results. Assessments of relatedness to AP1903/rimiducid should only apply for AEs which occur on or after the date of first rimiducid dose.

Adverse event severity missing: If the severity of an adverse event is missing, the severity will be assumed to be missing when summarizing data. Missing information will be reported as missing in the subject listings.

Non-study medication (concomitant medications, steroids) start and stop dates missing: If the start and/or stop dates of non-study medication use are incomplete or missing, the use will be assumed to be concomitant, unless the incomplete date information clearly indicates that the use stopped prior to the on-study-date. Missing or incomplete information will be reported as missing/incomplete in the subject listings.

For pharmacology and pharmacokinetic data, the following rules will be applied if there are values that are below the limit of quantitation (BLQ) or if there are missing values (e.g., no result [NR]) in a plasma concentration data series to be summarized.

- For the calculation of summary statistics, BLQ values will be set to zero.

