The resolution of acute GvHD (aGvHD) or chronic GvHD (cGvHD) after administration of rimiducid will be based on the response grading of the GvHD criteria provided in the protocol. The event for this endpoint is any patient who achieved a best overall response (BOR, i.e., either a Complete Response (CR) or Partial Response (PR)) based on aGvHD grading. Only patients experiencing aGVHD who received rimiducid (AP1903) infusion for treatment will be considered for this endpoint. Best overall resolution of aGVHD is defined from the date of AP1903 infusion. The percentage of patients with acute or chronic GvHD, the number of doses of rimiducid, and the best overall response to rimiducid within 7 and 30 days will be presented in listings and summarized. Concomitant medication usage in subjects with acute or chronic GvHD and, further, among those subjects who went on to receive rimiducid, will also be summarized.

Additional analysis and summary statistics will be conducted for resolution of chronic GvHD after administration of rimiducid as well as any case of GvHD (acute or chronic).

(iv) Immune reconstitution as determined by T cell subset counts at day 180

- a. Median and range of CD3 counts at 30, 60, 100 and 180 days
- b. Median and range of CD4 counts at 30, 60, 100 and 180 days
- c. Median and range of CD8 counts at 30, 60, 100 and 180 days

Quantitative assessment of each immune T-cell counts will be performed at various visit time points after transplant as captured in clinical database up to day 180 of follow-up. Analysis and statistical summaries will be performed separately for each T cell subtype assessed. The pattern of each immune reconstitution lab counts will be summarized using graphical summaries and descriptive statistic summary tables including mean (standard deviation), median, and range (minimum, maximum) across the time points assessed. Plots of mean and median cell counts representing measurements over time will be generated to visualize general patterns over time of immune reconstitution.

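### Rimiducid response is summarised as best response in two nested windows, so the 30-day rate cannot fall below the 7-day rate, and no planned table gives a rate of lost response among responders

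*SAP*

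**What the plan says.** The event in SAP 6.4.2(iii) is "any patient who achieved a best overall response (BOR, i.e., either a Complete Response (CR) or Partial Response (PR)) based on aGvHD grading". On timing, the SAP states: "Best overall resolution of aGVHD is defined from the date of AP1903 infusion". It does not say which infusion counts when a patient has more than one. The response rate is then summarised as the "best overall response to rimiducid within 7 and 30 days", for acute and chronic GvHD.

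The section sets no minimum duration, no confirmation and no rule for loss of response. The chronic GvHD response criteria in Protocol Appendix A.2 contain none either.

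The planned outputs on response (SAP 7.1.1) are Tables 14.2.4.1 to 14.2.4.3, on time to resolution, and Table 14.2.4.4, on best overall clinical response.

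The background in Protocol 4.1.3 says two things about the cells that survive rimiducid. The first is "The residual iCasp9 gene modified T cell population expanded over the next 4-14 days". The second is that the transduced cells contained "virus and fungal-peptide specific precursor cells which had not caused further GVHD".

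**The concern.** A pair of figures at 7 and 30 days is easily read as early response followed by response that has lasted. Best response in nested windows cannot carry that second meaning. A child with a partial response on Day 2 and full recurrence on Day 10 counts as a responder in both columns.

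Durability is a fair question for this product. Surviving cells can expand again over a period that straddles Day 7 and ends well inside the 30-day window. Protocol Appendix B also provides for recurrent chronic GvHD episodes. Evaluating rimiducid treatment of GvHD is the only secondary objective stated in SAP 3.1, and 6.4.2(iii) is the main analysis that serves it. As planned, that analysis could not show that responses were lost. It could not show that they lasted either, which the sponsor may well want to show.

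**Working it through.** The documents give no response rate, sample size or precision for this endpoint, so there is no figure to reproduce. The check is of the definition, followed by an illustration.

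**1. Can best response get worse between Day 7 and Day 30?** Take the chronic GvHD examination days after rimiducid in Appendix B: Days 1 and 2, "then weekly for 1 month, every 2 weeks for 100 days". In the first month this gives about Days 1, 2, 7, 14, 21 and 28. Let each visit show no response, PR or CR.

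- Possible patient paths: 3^6 = 729.
- Paths with CR or PR by Day 7 but not counted as CR or PR by Day 30: 0. The same holds for CR alone.
- Paths with a response by Day 7 and none at the last visit: (3^3 − 1) × 3^2 × 1 = 26 × 9 = 234. All 234 still count as 30-day responders.
- Paths moving from best PR by Day 7 to best CR by Day 30: (2^3 − 1) × (3^3 − 2^3) = 7 × 19 = 133. The PR-only row can therefore fall, but through improvement and not flare.

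**2. Does this depend on the denominator?** Yes. The SAP names none for this table. The natural choice is the Rimiducid Population in SAP 6.1, "Defined as all patients who received at least one dose of rimiducid for the treatment of acute or chronic GvHD", which is the same group for both windows. For patients who withdraw, SAP 6.2.2 says "all data attained up to the point of discontinuation will be listed and included in data summaries", so an early responder who leaves before Day 30 would stay counted. If such patients were dropped instead, the rate could fall: an assumed 14/20 = 70% becomes 12/18 = 67% with two dropped, or 10/16 = 62.5% with four. That fall would reflect dropout, not flare.

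**3. Illustration of size (all rates assumed).** Let r be best response by Day 7, L the share of Day-7 non-responders who first respond later and keep that response, and f the share of Day-7 responders who have flared by Day 30.

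- Planned 30-day figure: r + (1 − r)L
- Response present at Day 30: r(1 − f) + (1 − r)L
- Gap: r × f, whatever L is

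| r | L | f | Best response by Day 30 | Present at Day 30 | Gap (points) |
|---|---|---|---|---|---|
| 70% | 0 | 0 | 70% | 70% | 0 |
| 70% | 0 | 20% | 70% | 56% | 14 |
| 70% | 0 | 30% | 70% | 49% | 21 |
| 70% | 20% | 0 | 76% | 76% | 0 |
| 70% | 20% | 20% | 76% | 62% | 14 |

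Over r from 50% to 80% and f from 20% to 30%, the gap runs from 0.50 × 0.20 = 10 points to 0.80 × 0.30 = 24 points. At f = 0 it is nil.

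**4. How far does the earlier study settle f?** Protocol 4.1.3 describes skin GvHD resolving in all three patients and reports no further GvHD from the re-expanded cells. If three patients were treated (an assumption from that wording), 0 flares in 3 has a one-sided 95% upper limit of 1 − 0.05^(1/3) = 63%. Flare is not shown, and it is not excluded.

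**5. Does another planned table give the missing rate?**

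- Tables 14.2.4.1 to 14.2.4.3: reaching CR or PR is the event, so nothing after it is analysed.
- GvHD cumulative incidence (SAP 6.4.2(ii)) runs from transplant to GvHD and does not measure recurrence after response.
- EFS (SAP 6.4.1) uses the first event; later ones go to a listing.
- Tables 14.3.1.4.2 and 14.3.2.6 count adverse events and serious adverse events after rimiducid by preferred term and maximum severity. They do not separate responders who relapsed from patients who never responded.
- Listings 16.2.6.2.1 and 16.2.6.3 may show a flare in one patient but give no rate.

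**The case against.** The strongest reply is that a best-response rate that cannot fall is simply what best response means. The SAP never calls the 30-day figure sustained or durable, and under a time-to-resolution heading the two windows can be read as the share who have responded by each day. That stands: the SAP makes no false statement, and best response is a legitimate summary to keep.

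A reader might go further and infer that the plan does overstate benefit, because the cells re-expand. The documents do not support that. The only data they give on re-expansion report no further GvHD, and Protocol 4.1.3 adds that none of the ten patients developed chronic GvHD. The 70% and the flare rates above are assumptions, and zero flare gives no gap.

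Nor is later GvHD invisible. Protocol 9.1.5 has every occurrence reported and followed to resolution, SAP 6.5.1 promises specific GvHD tables and listings, and SAP 6.4.2(iii) summarises the number of rimiducid doses and concomitant medication. Protocol 10.4.5.3 also sets a 6-month response rate for chronic GvHD, without saying whether it means current status or best response. None of these gives a rate of lost response among responders by Day 30.

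Two limits of evidence also stand. The acute GvHD response criteria belong to the BP-004 protocol, which is not among the documents, so a duration rule there cannot be excluded. And the weekly examinations and the provision for recurrent episodes in Appendix B concern chronic GvHD, whereas the event definition in SAP 6.4.2(iii) rests on acute grading.

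**Conclusion.** The point holds in a limited form. With the same denominator in both windows, the planned 30-day CR+PR rate and CR rate cannot be lower than the 7-day rates, and no planned table gives the rate of lost response among responders. This follows from the definition and needs no assumed numbers, provided the BP-004 acute criteria contain no duration rule.

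The size is conditional. The overstatement of response still present at Day 30 equals the Day-7 response rate times the share of responders who flare: nil without flare, and 14 to 21 points at an assumed 70% response with 20% to 30% flaring. The documents do not establish that flare occurs, and they do not support discarding best response. The analysis is a descriptive secondary one in rimiducid-treated patients, and the primary EFS result does not depend on it. The gap is worth closing because this is the main analysis for the stated secondary objective and the addition is small.

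**What to change.** Keep best response within 7 and 30 days. Add to Table 14.2.4.4:

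- **Status.** CR or PR at the evaluation nearest Day 28-30 after the first rimiducid dose of the episode, relative to the grade before that dose, within a stated visit window. Count death or recurrence before then as non-response, and show missing evaluations separately.
- **Recurrence.** The number of responders with GvHD recurrence or worsening by Day 30.

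State the denominator, use it for every row, and report acute and chronic GvHD separately. For chronic GvHD, the month-1 examinations in Appendix B can supply the status. For acute GvHD no such schedule appears in these documents; the assessment days in SAP 4.4 run from transplant and not from rimiducid. The acute status should therefore use the GvHD grading records that are available, and the window should be set with that in mind.

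The cost is SAP wording, a little more derivation work and possibly a less favourable 30-day figure. No treatment rule or visit changes.

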**Table 1: Schedule of Events (Laboratory and Clinical)**

Time - Months (+/- 14 Days)	9	12	15	18	21	24	30	36	42	48	54	60	YEARLY	6-15
Overall Survival (OS)		X				X		X		X		X		X
Disease-Free Survival (DFS)		X				X		X		X		X		X
Relapse-Free Survival (RFS)		X				X		X		X		X		X
Hematology; Chemistry	X	X	X	X	X	X								
Immune Reconstitution  :	X	X	X	X	X	X								
RCR 	X	X	X	X	X	X	X	X	X	X	X	X		X
Modified History & Physical	X	X	X	X	X	X	X	X	X	X	X	X		X
Neurological Exam 	X	X	X	X	X	X	X	X	X	X	X	X		X
Vital Signs 	X	X	X	X	X	X								
GVHD Assessment 	X	X	X	X	X	X								
Concomitant Medication 	X	X	X	X	X	X								
Adverse Event	X	X	X	X	X	X	X	X	X	X	X	X		X
Bellicum Research Samples	BPX-501 T cell Assessment Research samples for assessment of BPX-501 cells (CD3+CD19+) will be collected monthly ( $\pm$ 14 days) until 1-year post BPX-501 infusion, every 6 months ( $\pm$ 1 month) for 24-months post BPX-501 infusion.													
	Post-systemic corticosteroid administration: Research samples (peripheral blood and/or tissue) for assessment of BPX-501 cells (CD3+CD19+) will be collected and sent to the sponsor prior to administration of systemic corticosteroids doses (e.g. methylprednisolone), at 4-hours ( $\pm$ 30 minutes) and 24-hours ( $\pm$ 1 hour) post-systemic corticosteroid initiation, and at 7-days, 14-days, 21-days, and 28-days ( $\pm$ 24 hours) post-systemic corticosteroid initiation.													
Rimiducid Infusion 	BPX-501 Cellular Kinetics (post-rimiducid) Within 4 hours ( $\pm$ 30 minutes) prior to initiation of rimiducid infusion, 30 minutes ( $\pm$ 5 minutes), then at 2 hours, 4 hours, 6 hours, 8 hours, 12 hours, and 24 hours ( $\pm$ 30 minutes) after initiation of infusion (of each dose of rimiducid) samples will be collected (and will be split for separate processing). Subsequently at 48 hours ( $\pm$ 1 hour) and 7 days (after initiation of infusion of each dose of rimiducid), and then at 14 days, 21 days, and 28 days ( $\pm$ 24 hours) after the final dose of rimiducid (if more than one dose is administered) blood samples will be drawn and evaluated for T cell responses only.													

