4.1. Definition of Study Drugs

The study drugs are:

- BPX-501: *Donor T cells genetically modified with BPZ-1001 retroviral vector containing the iC9 suicide gene, and*
- Rimiducid (AP1903): *Dimerizer drug used in case of a patient developing GvHD*

The BPX-501 T cell infusion is administered 14 days (+/-4 days) after completion of the stem cell allograft infusion. Under certain protocol versions, subjects may have been administered BPX-501 within 21 days (+/- 14 days) after completion of the stem cell allograft infusion. Subjects with uncontrolled Grade I or II skin-only, Grade II (non-skin), III, or IV acute GvHD were eligible to receive up to three doses of rimiducid at 0.4 mg/kg as a 2-hour intravenous (I.V.) infusion. Chronic GvHD, under conditions specified by protocol, will be treated with an infusion of rimiducid in individuals who have not previously received an infusion of rimiducid.

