Additional cell types and analytes for quantitative immunophenotyping include the absolute and relative numbers of CD3+CD19+ T cells (containing iC9), as well as the number of B cells, NK cells, and levels of IgA, IgM and IgG. In order to describe the pharmacodynamic effects of BPX-501 via proliferation of CD3+CD19+ cells, values post-rimiducid may be excluded. A separate analysis will examine CD3+CD19+ levels using the most recent samples available before and after treatment with rimiducid.

(v) *Time to immune reconstitution defined by CD3 count > 500 cells/uL; CD4 > 200 cells/uL or CD8 count of 200 cells/uL*

Time to immune reconstitution will be based on CD3, CD4 or CD8 counts for the defined thresholds above. Events are defined from the time of transplant to the time at which the threshold is achieved, with death considered as competing event. A patient not achieving the threshold T cell count will be censored on the last recorded visit day.

Time to immune reconstitution will be estimated using a Nelson-Aalen cumulative incidence function for each T cell subtype. Parameters estimates will be summarized for all subjects and by disease type (malignant or non-malignant). When estimable, additional summary statistics will include the median, minimum, maximum, the 25th and 75th percentiles of immune reconstitution, along with the number of events and censored observations. A cumulative incidence plot with descriptive summary statistics will be presented along with the number of patients at risk at various time points.

(vi) *Disease-Free/chronic GvHD-Free survival at 180 days*

The disease-free/chronic GvHD-free survival endpoint at 180 days will be assessed on the ITT (FAS) population. Events corresponding to disease-free/chronic GvHD-free survival outcomes include chronic GvHD, disease relapse for malignant subjects, disease recurrence for non-malignant subjects, or death by any cause. For patients with multiple events, the event that occurs first and the corresponding time will be used. Patients who do not experience an event will be censored on the last recorded visit day. Each patient outcome duration will be calculated from the date of transplant.

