- 14.2.1.5 Kaplan-Meier Parameter Estimates of Event-Free Survival: Sensitivity Analysis for Dose in Subjects with Malignant Disease
- 14.2.2 Cumulative Incidence Function Plot of Time to Transplant-Related or Non-Relapse Mortality
- 14.2.3.1.1 Cumulative Incidence Function Parameters Time to Acute GvHD: Grade 2 Organ, Grades 3-4
- 14.2.3.1 Cumulative Incidence Function Plot of Time to Acute GvHD Grades 2-4
- 14.2.3.2 Cumulative Incidence Function Plot of Time to Acute GvHD Grades 3-4
- 14.2.3.3.1 Cumulative Incidence Function Parameters Time to Moderate or Severe Chronic GvHD
- 14.2.3.3.2 Cumulative Incidence Function Plot of Time to Severe Chronic GvHD
- 14.2.3.3.3 Cumulative Incidence Function Plot of Time to Overall (Mild-to-Severe) Chronic GvHD
- 14.2.4.1 Kaplan-Meier Plot of Time to Resolution of Acute GvHD After Rimiducid Administration

- 14.2.4.2 Kaplan-Meier Plot of Time to Resolution of Chronic GvHD After Rimiducid Administration
- 14.2.4.3 Kaplan-Meier Plot of Time to Resolution of GvHD (Acute or Chronic) After Rimiducid Administration
- 14.2.5.1 Plot of of CD3 T Cell Counts Across Study Visit Time Points to 180 Days
- 14.2.5.2 Plot of of CD4 T Cell Counts Across Study Visit Time Points to 180 Days
- 14.2.5.3 Plot of of CD8 T Cell Counts Across Study Visit Time Points to 180 Days
- 14.2.5.4.1 Plot of CD3+CD19+ T Cell Counts Across Study Visit Time Points to 180 Days
- 14.2.5.4.2 Plot of the Proportion of CD3+CD19+ T Cells Across Study Visit Time Points to 180 Days
- 14.2.5.4.3 Plot of CD3+CD19+ T Cell Counts Before and After Treatment with Rimiducid
- 14.2.5.4.4 Plot of the Proportion of CD3+CD19+ T Cells Before and After Treatment with Rimiducid
- 14.2.5.5 Plot of B Cell Counts Across Study Visit Time Points to 180 Days
- 14.2.5.6 Plot of NK Cell Counts Across Study Visit Time Points to 180 Days
- 14.2.5.7 Plot of Immunoglobulin A Levels Across Study Visit Time Points to 180 Days
- 14.2.5.8 Plot of Immunoglobulin M Levels Across Study Visit Time Points to 180 Days
- 14.2.5.9 Plot of Immunoglobulin G Levels Across Study Visit Time Points to 180 Days
- 14.2.6.1 Cumulative Incidence Function Plot of Time to Immune Reconstitution of CD3 T-cell Count
- 14.2.6.2 Cumulative Incidence Plot of Time to Immune Reconstitution of CD4 T-cell Count
- 14.2.6.3 Cumulative Incidence Plot of Time to Immune Reconstitution of CD8 T-cell Count
- 14.2.7 Kaplan-Meier Plot of Time to Disease-Free/Chronic-GvHD-Free Survival

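### CD3+CD19+ (BPX-501) cells are displayed by time from transplant, so the permitted infusion windows put 8 or 28 days of spread into time since infusion and blur the early expansion curve

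*SAP*

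**What the plan says.** SAP 6.4.2 (iv) sets the time axis for the T-cell summaries: "Quantitative assessment of each immune T-cell counts will be performed at various visit time points after transplant". CD3, CD4 and CD8 counts are tabulated at 30, 60, 100 and 180 days. The section then adds CD3+CD19+ cells, in absolute and relative numbers, as further analytes. The reason given for handling these values specially is pharmacodynamic: "In order to describe the pharmacodynamic effects of BPX-501 via proliferation of CD3+CD19+ cells", after which the SAP allows values following rimiducid to be left out. Samples taken before BPX-501 infusion are not mentioned.

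SAP 7.1.1 lists Figure 14.2.5.4.1, "Plot of CD3+CD19+ T Cell Counts Across Study Visit Time Points to 180 Days", and Figure 14.2.5.4.2, the same display for the proportion of these cells. SAP 6.2.3 and 6.3.4 count study days from the stem cell transplant.

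Infusion timing is in SAP 4.1. The general rule is "The BPX-501 T cell infusion is administered 14 days (+/-4 days) after completion of the stem cell allograft infusion". The exception, under certain protocol versions, is that "subjects may have been administered BPX-501 within 21 days (+/- 14 days) after completion of the stem cell allograft infusion". The per-protocol population accepts either window: "within a dosing around Day 14 (+/- 4 days) or Day 21 (+/- 14 days) after HSCT". The full analysis set sets a dose criterion only ("The FAS/ITT population includes all patients treated with HSCT who received BPX-501 at the dose of" 1×10^6 cells/kg) and places no limit on the day of infusion.

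**The concern.** CD3+CD19+ cells are the product. How fast they appear, how high they rise and when they peak are functions of time since BPX-501 was infused, not of time since the stem cells were given. If infusion fell on the same day in every patient, the two clocks would differ by a constant and the choice would not matter. The SAP permits infusion over a range of days and pools the data, so a single visit can combine patients at different stages of expansion and, at early visits, patients not yet infused.

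At stake is the SAP's own pharmacodynamic description of BPX-501. A mean or median curve on the transplant clock is flattened and spread out by variation in infusion day, and a reader cannot separate that from true variation in expansion.

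Elsewhere the SAP does use the clock of the treatment concerned. Treatment-emergent adverse events (6.5) and concomitant medications (6.3.7) are defined from BPX-501 infusion, and resolution of GvHD after rimiducid is measured from the rimiducid infusion (6.4.2 (iii)). Sensitivity outputs by dosing window are listed for event-free, disease-free and relapse-free survival (7.1.1), but none for CD3+CD19+ cells.

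**Working it through.** The plan states no figure to reproduce; the check is date arithmetic.

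Inputs:
- Standard window, Day 14 ± 4 (SAP 4.1): 14 − 4 = Day 10 to 14 + 4 = Day 18.
- Wide window, Day 21 ± 14 (SAP 4.1): 21 − 14 = Day 7 to 21 + 14 = Day 35.
- Nominal visits at Days 14, 30, 60, 100 and 180, with stem cells given on Day 0 (SAP 4.4).

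Formula: days since infusion = visit day − infusion day, taken at each end of the window. For Day 30, the standard window gives 30 − 18 = +12 to 30 − 10 = +20. The wide window gives 30 − 35 = −5 to 30 − 7 = +23.

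| Nominal visit | Day 14 ± 4 | Day 21 ± 14 |
|---|---|---|
| Day 14 | −4 to +4 | −21 to +7 |
| Day 30 | +12 to +20 | −5 to +23 |
| Day 60 | +42 to +50 | +25 to +53 |
| Day 100 | +82 to +90 | +65 to +93 |
| Day 180 | +162 to +170 | +145 to +173 |

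The spread is 18 − 10 = 8 days or 35 − 7 = 28 days at every visit. Counting the transplant as Day 0 or Day 1 shifts both terms equally and leaves the differences unchanged.

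The relative effect shrinks with time. The ratio of longest to shortest time since infusion is:
- Day 30, standard window: 20/12 = 1.67 (no ratio is defined for the wide window, which includes negative times).
- Day 60: 50/42 = 1.19, or 53/25 = 2.12.
- Day 180: 170/162 = 1.05, or 173/145 = 1.19.

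Within the stated windows, pre- and post-infusion samples can mix at Day 14 under either window, and at Day 30 only under the wide one. From Day 60 every sample is post-infusion.

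The share of Day 30 samples taken before infusion cannot be computed, because infusion days are not reported. It is 0% if everyone followed Day 14 ± 4. If, purely for illustration, infusion days were uniform over Days 7 to 35, it would be 5 of 29 days (Days 31 to 35), or about 17%.

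**The case against.** Several points on the other side have force.

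First, the wide window is an exception. Under the standard rule no nominal Day 30 sample precedes infusion and the spread is 8 days. This stands, and it limits the size of the problem, but the SAP covers the versions with the wide window and accepts it even in the per-protocol population.

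Second, it is not certain that Day 14 values will be shown. The tabulated points for CD3, CD4 and CD8 start at Day 30, the figures refer only to study visits, and the detailed BP-004 schedule is not among the documents. This stands too: the Day 14 mixing applies only if those values are summarised.

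Third, the transplant clock has a legitimate use. On the same axis as CD3, CD4 and CD8, CD3+CD19+ counts show what the product contributes to reconstitution at each visit. That is a reason to keep those plots. It does not make them suitable for describing proliferation.

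A reader might also infer a mismatch with the sampling clock from BP-404 protocol Table 1, where "Research samples for assessment of BPX-501 cells (CD3+CD19+) will be collected monthly" and the schedule is counted from BPX-501 infusion. The documents do not support that for these figures: BP-404 enrols patients beyond Day 180, and the figures stop at Day 180. Table 1 shows only that the infusion clock is already used in the programme.

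**Conclusion.** The point holds as a modest, cheaply corrected weakness in a secondary, descriptive analysis. On the planned axis, time since infusion differs between patients by up to 8 days under the standard window and 28 days under the wide one. The onset and peak of CD3+CD19+ expansion are blurred, and nothing in the SAP re-anchors these summaries to infusion or removes pre-infusion samples. The figures assume nominal visit days and infusion within the stated windows. Visit windows for BP-004 are not given and would widen the spread, as would infusions outside the windows, which the full analysis set does not exclude.

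Four stronger readings are not supported:
- That infusion actually ranged over Days 7 to 35. This is what certain versions permitted; no observed infusion days are reported.
- That the clock produces a particular fold difference in counts. That would need a doubling time, which the documents lack. The 4 to 14 days in protocol 4.1.3 describes how long residual cells re-expanded after rimiducid in another trial, not a growth rate after first infusion.
- That comparisons by dose are confounded. Secondary analyses use the full analysis set (SAP 6.4), which is limited to one dose. Confounding by disease group would require infusion timing to differ between groups, which is not shown.
- That persistence cannot be read. By Day 180 all samples are 145 to 173 days after infusion.

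The primary event-free survival analysis is unaffected.

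**What to change.** In SAP 6.4.2 (iv), for CD3+CD19+ counts and proportions, add a display and summary by actual days since BPX-501 infusion, calculated as sample date minus infusion date. Either make it the primary pharmacodynamic description or present it beside Figures 14.2.5.4.1 and 14.2.5.4.2. State that pre-infusion samples are excluded from the proliferation summary or shown as baseline, and carry over whatever rule is adopted for post-rimiducid values.

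Choose the summary windows to match the samples available. Under the standard window the nominal visits from Day 30 fall at 12 to 20, 42 to 50, 82 to 90 and 162 to 170 days after infusion, so windows centred on round post-infusion days such as 30 or 60 could be nearly empty. No nominal visit up to Day 180 reaches 180 days after infusion within the stated windows (the maximum is 173). A plot of individual values against actual days avoids the difficulty.

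Keep the transplant-clock plots alongside CD3, CD4 and CD8.

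The cost is a short SAP addition and one extra set of outputs. Infusion data are already planned for Listing 16.2.5.2, and SAP 6.3.4 has listings carry assessment dates, so no new data collection is needed.
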